### 7.6.2.3 SARS-CoV-2 PCR Test

Time to virological clearance, measured as study days from start of treatment to first negative SARS-CoV-2 PCR test, will be evaluated using similar statistical methods as clinical improvement where in this case, the first negative SARS-CoV-2 PCR test is considered as an event. Patients will be censored on Day 28 if they have not yet shown SARS-CoV-2 PCR negative or have died by Day 28.

If quantitative SARS-CoV-2 PCR results are available, the following analyses will be conducted. Note that if a patient has tested negative, they are assumed to be negative until they are tested again and for negative test result, viral load is assumed to be half of the lower limit of detection.

- Rate of change in viral load will be estimated using a Mixed Model for Repeated Measurements model.

The model will include the treatment group, age at baseline ( $> 65$  years vs  $\leq 65$  years), remdesivir or other authorized treatments for COVID-19 use at baseline (yes vs no), log (viral load) at baseline, study day (numerical, 0 for baseline), and the interaction between study day and the treatment group as fixed factors, patient as random factor (random intercept and random slope).

The model will use natural-log-transformed viral load as the response variable.

An unstructured covariance structure will be used. In case of a convergence problem with the unstructured covariance matrix, the following structures with robust sandwich estimator for the standard error of the fixed effect estimates will be assessed in a sequential fashion: heterogeneous Toeplitz, heterogeneous first-order autoregressive, Toeplitz and compound symmetry.

The estimate of the study day\*treatment will be interpreted as the difference between treatment and placebo groups in terms of the rate of change in viral load. The estimate, standard error and p-value of study day\*treatment will be reported.

- Natural-log-transformed viral load with change from baseline will be summarized by treatment group and visit using descriptive statistics.
- Arithmetic mean (+SD) of natural-log-transformed viral load vs. time figure for each treatment group will be presented.

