8.3. General Considerations

Continuous variables will be summarized by the standard descriptive statistics: number of patients (n), mean, standard deviation, median, minimum, and maximum. Frequency of patients or events and percentages will be summarized in categorical variables.

Missing values on clinical improvement score will be imputed using Last Observation Carried Forward for a maximum of 1 day at Day 7, 2 days at Day 14, and 4 days at Day 28. For

respiratory failure status, where a patient has died, their status will not be considered missing but will be treated as an observation at each timepoint.

Unless otherwise stated, all regression models will be adjusted for age and remdesivir or other authorized treatments for COVID-19 use at baseline.

Results will be considered statistically significant at one-sided alpha of 0.025, and considered to indicate promising trend at one-sided alpha of 0.2.

Additional information is available in the statistical analysis plan (SAP).

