8.4.2. Secondary efficacy outcome measures

Clinical improvement measured as a score on the WHO COVID-19 Clinical Improvement Ordinal Scale will be analyzed at each timepoint, adjusted for the clinical improvement score at baseline, age at baseline, and remdesivir or other authorized treatments for COVID-19 use at baseline, using an ordinal logistic regression on Days 7, 14, and 28. In addition, descriptive statistics will be provided for average score, and the proportion of patients at or below each score, at each timepoint. Time to 2-point improvement from baseline in WHO COVID-19 Clinical Improvement score, time to score of 2 or lower, and time to score of 0, will also be analyzed.

The hazard ratio and its 95% confidence interval for time to event outcomes will be estimated by Cox proportional hazard model, with patients censored at the time they are provided any antiviral therapy not prescribed at baseline, or on Day 28 if they have not yet recovered. Patients who die at any time will be considered not yet recovered by Day 28. Median time to 2-point improvement, time to score of 2 or lower, and time to score of 0 will be estimated by Kaplan-Meier (KM) method, and the KM curve will be provided. The p-value for comparison between groups will be obtained based on proportional hazards modeling stratified by the same covariates as the primary model.

Duration of hospitalization and ICU stay up to Day 28 will be analyzed using normal regression, using the same covariates as for the primary endpoint. Patients who die will be considered as continuing to require hospitalization or ICU stay up to Day 28 for the purposes of this analysis.

Time to virological clearance, measured as study days from start of treatment to first negative SARS-CoV-2 PCR test, will be evaluated using similar statistical methods as clinical

improvement. All patients who have died will be considered as not having cleared the virus by Day 28

Rate of change in viral load will be summarized descriptively and estimated using a Mixed Model for Repeated Measurements model. The model will include the treatment group, age, remdesivir or other authorized treatments for COVID-19 use at baseline, visit, and the interaction between visit and the treatment group as fixed factors, and will include the baseline value as a covariate. If a patient has tested negative, they are assumed to be negative until they are tested again.

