### 2.3 Sample Size

A total of 174 patients are planned to be randomized into the study:

- 20 patients in the sentinel cohort (10 patients in each treatment group)
- 154 patients in the expansion cohort (77 patients in each treatment group).

This enrollment level ensures 80% power to demonstrate proof of concept efficacy with one-sided alpha of 0.2.

The sample size is based on the following assumptions:

- The randomized allocation ratio is 1:1 between the antroquinonol group and the placebo group
- The proportion of patients alive and free of respiratory failure is approximately 78% on placebo vs 89% on antroquinonol

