#### 7.6.2 Secondary Efficacy Analysis

##### 7.6.2.1 Clinical Improvement Score as Measured by WHO COVID-19 Clinical Improvement Ordinal Scale

Clinical improvement measured as a score on the WHO COVID-19 Clinical Improvement Ordinal Scale will be analyzed using an ordinal logistic regression on Days 7, 14, and 28, with study treatment, clinical improvement score at baseline (as numerical variable), age at baseline ( $> 65$  years vs  $\leq 65$  years), and remdesivir or other authorized treatments for COVID-19 use at baseline (yes vs no) as covariates. The p-value for treatment effect will be provided based on the Wald test.

In addition, descriptive statistics will be provided for average score by treatment group, and the proportion of patients at or below each score, at each visit.

Time to 2-point improvement from baseline in WHO COVID-19 Clinical Improvement score, time to score of 2 or lower, and time to score of 0, will also be analyzed. The hazard ratio and its 95% confidence interval for these time-to-event endpoints will be estimated by Cox proportional hazard model, with treatment, remdesivir or other authorized treatments for COVID-19 use at baseline (yes vs no) and age at baseline ( $> 65$  years vs  $\leq 65$  years) as covariates. The analysis will be carried out using two different censoring rules: 1) Patients will be censored at the time they are provided any authorized treatment for COVID-19 not prescribed at baseline, or on Day 28 if they have not yet recovered or have died by Day 28; 2) Patients will only be censored on Day 28 if they have not yet recovered or have died by Day 28. The p-value for comparison between treatment groups will be obtained based on the Cox proportional hazards model described above. Median time to 2-point improvement, time to score of 2 or lower, and time to score of 0 will be estimated by Kaplan-Meier (KM) method, and the KM curve will be provided.

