## Statistical Analysis Plan

Sponsor Name: Golden Biotechnology Corporation  
Sponsor Protocol ID: GH Covid-2-001

Covance Study ID: 000000203201

- h Efficacy parameter assessments: [1] Confirmation of whether the patient is discharged to home, is in the hospital, or has worsened to require an ICU. The number of days a patient has been hospitalized prior to study entry will be recorded in the eCRF. [2] PCR testing for SARS-CoV-2 will be performed by a local or central laboratory at screening. Results of confirmatory COVID-19 test already done as standard of care can be used to determine eligibility. All subsequent tests will be performed by a central laboratory at baseline/Day 1, Day 5 and Day 14. Also at Follow-up/EOS if patient is hospitalized. Either nasopharyngeal or mid-turbinate samples are allowed for central testing. Only one method should be used throughout the study for the participant. [3] Clinical improvement score will be measured using the WHO COVID-19 Clinical Improvement Ordinal Scale (refer to Appendix 7 of the protocol). [4] Patient mortality will be recorded up to Day 28. Every effort will be made to ascertain vital status in all randomized patients (e.g., with a vital records search) up to Day 28. [5] Respiratory failure is considered as patient need for invasive mechanical ventilation, non-invasive ventilation, high-flow oxygen, or ECMO. The date of the start of the respiratory intervention must be recorded in the eCRF; no daily assessment is needed. [6] COVID-19 symptoms (presence or absence of dry cough, dyspnea (shortness of breath/ difficulty in breathing), or chills/rigors, myalgia (muscle pain), headache, sore throat, and loss of taste or smell; other symptoms that could be related to COVID-19) will also be assessed during hospitalization, on discharge, ET/EOT and Follow-up/EOS visit (at the site, home visit, or via telephone or telemedicine if patient has been discharged).

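### Time to virological clearance is to be fitted with a Cox model without a stated tie method, although swabs fall on only two or three visits; under Breslow ties the hazard ratio would be pulled toward 1

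*SAP*

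**What the plan says.** Protocol 8.4.2 defines the endpoint as "Time to virological clearance, measured as study days from start of treatment to first negative SARS-CoV-2 PCR test". SAP 7.6.2.3 adds that it "will be evaluated using similar statistical methods as clinical improvement where in this case, the first negative SARS-CoV-2 PCR test is considered as an event". The method referred to is in SAP 7.6.2.1: "The hazard ratio and its 95% confidence interval for these time-to-event endpoints will be estimated by Cox proportional hazard model", with treatment, baseline COVID-19 treatment and age group as covariates, plus a Kaplan-Meier median.

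The sampling is sparse. SAP Appendix 2, footnote h, states: "All subsequent tests will be performed by a central laboratory at baseline/Day 1, Day 5 and Day 14". The same footnote adds a Follow-up swab only for patients in hospital. SAP 6.1 sets the windows at Days 4-6, 14-16 and 26-30.

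SAP 7.1 names SAS 9.4 or later. Neither document names a tie method, a grouped-time model or an interval-censored model.

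**The concern.** A Cox model is built for event times that are mostly distinct. Here a patient who clears at any time between Day 1 and the first swab is dated to Day 4, 5 or 6, and one who clears between the two swabs to Day 14, 15 or 16. That leaves six possible dates for a patient who has gone home. When a large share of the risk set has its event on one date, the choice of tie approximation changes the estimate materially, and the plan leaves that choice open.

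Two smaller problems exist under any tie method. A Day 4 swab counts as earlier clearance than a Day 6 swab, although the difference is appointment timing. And the Kaplan-Meier median can only land on a test day or not be reached.

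At stake is a secondary antiviral comparison. The other virological measure, the viral-load slope, depends on quantitative assays being available, so time to clearance may be the only between-group antiviral test.

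**Working it through.** **Inputs from the documents.** 174 patients with equal allocation ("The randomized allocation ratio is 1:1 between the antroquinonol group and the placebo group", SAP 2.3), so 174/2 = 87 per arm. Test levels, Protocol 8.3: "Results will be considered statistically significant at one-sided alpha of 0.025, and considered to indicate promising trend at one-sided alpha of 0.2".

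**Assumed, because the documents give no figures.** True hazard ratio 1.5; placebo clearance by Day 5 and Day 14 of 30%/80% or 20%/60%; no deaths or dropout; treatment as the only covariate.

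**The plan's own figure.** No power, event count or hazard ratio is stated for clearance. The one power statement concerns the primary endpoint: "This enrollment level ensures 80% power to demonstrate proof of concept efficacy with one-sided alpha of 0.2", with "The proportion of patients alive and free of respiratory failure is approximately 78% on placebo vs 89% on antroquinonol". The variance of the log odds ratio is 1/(87 × 0.78 × 0.22) + 1/(87 × 0.89 × 0.11) = 0.0670 + 0.1174 = 0.1844, so the standard error is 0.4294. The final boundary is exp(−0.8416 × 0.4294) = 0.697, as in Protocol 8.1. Simulated power with both futility looks applied is 81.0%. The primary design reproduces, and nothing below touches it.

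**Step 1: what Breslow estimates at one tied date.** With d1 of n1 and d0 of n0 having the event, the score equation is d1/(d1 + d0) = n1θ/(n1θ + n0). Its solution is θ = (d1/n1)/(d0/n0), which is the risk ratio and not the hazard ratio. Under proportional hazards the active-arm risk in an interval is 1 − (1 − p)^1.5, where p is the placebo risk among those not yet cleared.

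| Placebo clearance | Interval | p | Active risk | Risk ratio |
|---|---|---|---|---|
| 30%/80% | to Day 5 | 0.300 | 0.414 | 1.38 |
| 30%/80% | Day 5 to 14 | 0.50/0.70 = 0.714 | 0.847 | 1.19 |
| 20%/60% | to Day 5 | 0.200 | 0.284 | 1.42 |
| 20%/60% | Day 5 to 14 | 0.40/0.80 = 0.500 | 0.646 | 1.29 |

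**Step 2: pooling the two dates.** For 30%/80%, the expected active events are 36.05 + 43.17 = 79.22. The totals are 62.15 events with 87 at risk in each arm, then 86.67 events with 50.95 active and 60.9 placebo patients at risk. Solving 79.22 = 62.15·θ/(θ + 1) + 86.67·50.95θ/(50.95θ + 60.9) gives θ ≈ 1.26 (34.69 + 44.53 = 79.22). For 20%/60% the same equation gives θ ≈ 1.34. Simulation gives 1.27 and 1.33. The attenuation therefore follows from the tie formula.

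**Step 3: simulation on the plan's schedule (Day 5 and Day 14), 87 per arm.** Ranges cover the two clearance assumptions.

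| Analysis | Swab days | Mean HR | Power at one-sided 0.025 |
|---|---|---|---|
| Cox, Breslow | all on target day | 1.27-1.33 | 21-27% |
| Cox, Breslow | spread over windows | 1.36-1.43 | 45-49% |
| Cox, Efron | either | 1.44-1.49 | 55-62% |
| Grouped-time cloglog | either | about 1.5 | 57-67% |

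At one-sided 0.2, with swabs spread, power for Breslow, Efron and cloglog is 89%, 92% and 94% (30%/80%), or 88%, 91% and 91% (20%/60%). With every swab on target, Breslow has 82-84% and cloglog 90-93%.

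**Step 4: why the test is conservative.** Take a variant in which everyone is also tested at Day 28, with 60% of placebo cleared by Day 14 and swabs on target days. Breslow's average model-based standard error is 0.162, but its estimates vary with standard deviation 0.116. Power is about Φ[(ln HR/SE − 1.96)/(SD/SE)]:

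- Breslow: ln 1.329/0.162 = 1.756; (1.756 − 1.96)/0.716 = −0.285; 39%.
- Cloglog: ln 1.510/0.167 = 2.468; (2.468 − 1.96)/1 = 0.508; 69% (simulated 70%).
- Efron, simulated: HR 1.47, 68%.

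With no true effect, Breslow on target days rejected in 0.1-0.9% of trials at a nominal 2.5%. It makes no excess of false claims.

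**Step 5: events dated on any calendar day.** In the Step 4 setting, Breslow gives HR 1.48 with 69% power and Efron 1.51 with 72%. Across 40-80% clearance, day-level ties cost Breslow about 1 to 5 points.

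**The case against.** The strongest reply is that the cause is an unstated option and not the Cox model. This stands. Under Efron ties the hazard ratio stays at 1.44-1.49 and power comes close to that of the grouped-time model. That Breslow would be used when nothing is specified is my assumption. One clause naming Efron or exact ties would remove most of the problem.

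Second, the trial was sized at one-sided 0.2, and Protocol 8.3 treats that level as a promising trend. There the loss is small. This also stands. A reader might infer that a real antiviral effect would probably be missed; at 0.2, with a hazard ratio of 1.5, Breslow still has more than 80% power. The large loss applies only at 0.025, which the plan reserves for statistical significance.

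Third, time is counted in actual study days, so the windows break up some ties. That is right, and the target-day figures are the worst case. Spreading reduces the attenuation but does not remove it. Within-window timing in a blinded trial adds noise; it does not favour an arm.

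Fourth, a reader might extend the point to all the WHO-score times. The documents do not support that. Both schedules record the scale at Day 3 and at discharge on any day from 2 to 28, and SAP 6.2 sets a missing score to 2 on the day after discharge. Score 2 or lower, and 2-point improvement from a baseline score of 4, are therefore largely dated by discharge, where Step 5 shows little loss. Time to score 0 is the exception: Protocol Appendix 7 requires no virological evidence of infection, which is dated at visits.

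Finally, Cox and Kaplan-Meier are specified in Protocol 8.4.2, so replacing them is a change that must be recorded.

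**Conclusion.** The point holds for time to virological clearance. The plan leaves the tie method open on data where it matters: with the same swabs, the average hazard ratio is about 1.27-1.43 under Breslow and 1.44-1.49 under Efron, against an assumed truth of 1.5. At one-sided 0.025, Breslow has 21-49% power and the grouped-time model 57-67%; at 0.2 the gap is about 2-11 points. The direction is conservative.

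These figures rest on an assumed hazard ratio, assumed clearance rates and the assumption that Breslow would be applied. The endpoint is secondary with no stated power target, and the documents do not rank it as the main antiviral result. The primary analysis and N = 174 are unaffected. The grouped-time model is still preferable to Efron ties because it does not read appointment timing as earlier clearance. Adding the visit proportions answers the stated objective of clearance on Days 5, 14 and 28, for which SAP 7.6.2.3 plans no proportion by visit.

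**What to change.** In SAP 7.6.2.3, analyse clearance with a grouped-time proportional hazards model: binomial regression with complementary log-log link, intervals ending at the Day 5, Day 14 and Day 28 visits, and the same covariates. Patients contribute only the intervals in which they were tested, so discharged patients do not count as tested at Day 28; state a rule for a missed Day 5 swab. Report the proportions cleared by Day 5 and by Day 14. At minimum, specify Efron or exact ties.

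In SAP 7.6.2.1, keep one Cox model each for 2-point improvement and for score 2 or lower, and name Efron or exact ties. For time to score 0, use the grouped-time model or exact ties.

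Record the departure from Protocol 8.4.2 in SAP Section 8, which now declares no changes. The cost is SAP wording and a few lines of code. No new data are needed, and the effect measure stays a hazard ratio.

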### 3.2 Secondary Efficacy Endpoints

- Clinical improvement score as measured by the WHO COVID-19 Clinical Improvement Ordinal Scale, as follows:
  - Time to 2-point improvement from baseline.
  - Supportive analysis, time to score 2 or lower.
  - Supportive analysis, time to score 0.
- Duration of hospitalization (days) up to Day 28
- Virological clearance evaluated using PCR testing from nasopharyngeal or mid-turbinate samples on Day 5, 14, and 28:
  - Time to virological clearance, measured as study days from start of treatment to first negative SARS-CoV-2 PCR test
  - Rate of change in viral load will be evaluated depending on availability of quantitative assays.
- Vital status (death) on Days 7, 14, and 28
- Duration of ICU stay up to Day 28
- Proportion of patients alive and free of respiratory failure on Days 7 and 28
- COVID-19 symptoms on Days 7, 14, and 28. Assessment will evaluate: presence or absence of dry cough, dyspnea (shortness of breath/ difficulty in breathing), or chills/rigors, myalgia (muscle pain), headache, sore throat, and loss of taste or smell; other symptoms that could be related to COVID-19 will also be recorded.

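### The Cox model for time to virological clearance leaves out baseline viral load, a covariate the SAP already uses in the same section; the test is valid but loses efficiency if load is prognostic

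*SAP*

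**What the plan says.** **Clearance endpoint.** SAP 7.6.2.3 defines the analysis by reference: time to clearance "will be evaluated using similar statistical methods as clinical improvement where in this case" the event is the first negative test. It lists no covariates of its own.

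**Model referred to.** In SAP 7.6.2.1 the hazard ratio for the time-to-event endpoints "will be estimated by Cox proportional hazard model, with treatment, remdesivir or other authorized treatments for COVID-19 use at baseline (yes vs no"), with age above or below 65 as the remaining term. Protocol 8.3 names the same two adjusters as the default: unless otherwise stated, "all regression models will be adjusted for age and remdesivir or other authorized treatments for COVID-19 use at baseline".

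**Viral-load model.** The mixed model in SAP 7.6.2.3 contains the same two factors and also "log (viral load) at baseline, study day (numerical, 0 for baseline"). The section sets negative results to half the lower limit of detection and works on the natural-log scale.

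**Condition.** That block applies only in one case: "If quantitative SARS-CoV-2 PCR results are available, the following analyses will be conducted". SAP 3.2 says the same of the endpoint: "Rate of change in viral load will be evaluated depending on availability of quantitative assays".

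**The concern.** The event is a fall below the assay's detection limit. For a given rate of decline, a patient who starts higher should take longer to reach it, so baseline load is a natural candidate for a strong predictor. Starting loads may vary widely: Protocol 4.1 allows symptom onset up to two weeks before randomisation, and Protocol 7 accepts a documented earlier test. Randomisation is stratified only by age and authorised treatment (Protocol 5.3), so load is balanced in expectation but not by design.

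Leaving a strong predictor out of a Cox model attenuates the treatment HR relative to the conditional HR and costs power. Protocol 1.1 lists suppression of the virus among the trial's goals, and this endpoint bears on it directly. The covariate would come from the Day 1 central-laboratory PCR that is already scheduled, and the SAP already fixes its scale and its rule for negatives.

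**Working it through.** **Step 1: is the covariate really absent?** The covariate sets, side by side:

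| Analysis | Age, authorised treatment | Baseline value of the outcome |
|---|---|---|
| Ordinal regression of WHO score (SAP 7.6.2.1) | yes | yes, baseline score |
| Cox models for clinical improvement (SAP 7.6.2.1) | yes | no |
| Cox model for clearance (SAP 7.6.2.3, by reference) | yes | no |
| Viral-load mixed model (SAP 7.6.2.3) | yes | yes, log baseline load, if quantitative PCR exists |

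The word *similar* leaves some room, but Protocol 8.3 supports this reading. Baseline viral load is in no Cox model.

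**Step 2: the plan's own figure.** Neither document gives an HR, event count or power for clearance. The only power figure, 80% at one-sided 0.2, belongs to the binary primary endpoint and has no bearing here.

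**Step 3: size of the loss, by simulation.** From the documents: 174 patients, 1:1, so 87 per arm; one-sided levels 0.025 and 0.2; PCR on Days 5 and 14, and on Day 28 only for patients still in hospital (SAP Appendix 2, note h).

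Assumed, because the documents are silent: hazard of clearance = base rate × exp(log(1.5) × treatment − b × z), where z is standardised log load and exp(b) is the prognostic HR per SD. Each simulated trial was fitted by a Cox model (Efron ties) with and without z. The two simulations bracket the Day 28 schedule:

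- *A*: base rate log(2)/12 per day (placebo median 12 days at average load); PCR on Days 5, 14 and 28 for all; age and treatment-use terms in both models; no deaths or dropout; 1,500 trials per setting.
- *B*: 60% of placebo negative by Day 14; PCR on Days 5 and 14 only; 2,500 trials per setting.

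Results, without → with baseline load:

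| Prognostic HR per SD | Simulation | Estimated HR | Power, one-sided 0.025 | Power, one-sided 0.2 |
|---|---|---|---|---|
| 1.0 | A | 1.480 → 1.484 | 67.7% → 68.4% | 94.4% → 94.1% |
| 1.25 | A | 1.469 → 1.487 | 64.4% → 66.9% | 93.8% → 94.4% |
| 1.35 (exp 0.3) | B | 1.47 → 1.49 | 53% → 56% | 89% → 91% |
| 1.5 | A | 1.433 → 1.478 | 58.1% → 63.5% | 91.2% → 94.1% |
| 1.82 (exp 0.6) | B | 1.40 → 1.46 | 44% → 53% | 84% → 88% |
| 2.0 | A | 1.371 → 1.463 | 45.3% → 60.8% | 84.8% → 92.1% |
| 2.5 | A | 1.328 → 1.444 | 37.7% → 55.2% | 78.5% → 91.1% |
| 2.72 (exp 1.0) | B | 1.33 → 1.42 | 33% → 46% | 75% → 86% |

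Monte Carlo error in A is about 1 point. The range across settings with prognostic load:

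- One-sided 0.025: from 66.9 − 64.4 = 2.5 to 55.2 − 37.7 = 17.5 points.
- One-sided 0.2: from 94.4 − 93.8 = 0.6 to 91.1 − 78.5 = 12.6 points.
- HR: from 1.487 − 1.469 = 0.018 to 1.444 − 1.328 = 0.116.

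With non-prognostic load, B gives 90.6% and 90.3% for the two models at one-sided 0.2, so nothing is lost there either.

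**Step 4: is the planned test valid?** With true HR 1.0, simulation A gives estimated HRs of 0.994 to 1.001. Rejection rates for both models are 1.8% to 2.7% at one-sided 0.025 and 18.1% to 20.5% at one-sided 0.2. B gives 20% to 22% at one-sided 0.2 (500 trials). Both models are near nominal.

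**Step 5: chance imbalance.** The standard error of the difference in mean standardised load is √(2/87) = 0.15 SD. With b = 0.6, a one-standard-error imbalance moves the log HR by 0.6 × 0.15 = 0.09, against log(1.5) = 0.41. This is ordinary sampling variation, which the planned test already allows for; adjustment reduces it.

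**The case against.** The strongest reply is that this is an optional gain resting on things the documents do not establish. Much of it stands.

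- **Prognostic strength is nowhere stated.** This stands. A reader might infer that power is certainly lost; the documents do not support that, and at the weak end the gain is 0 to 3 points.
- **Quantitative PCR may not exist.** This stands. Clearance needs only positive or negative results, and a covariate set that is always available is a defensible default. The remedy has to be conditional.
- **The test is sound.** This stands. A reader might infer that the planned HR is biased or that imbalance in load inflates false positives. Step 4 shows neither: the HR without load validly estimates a less conditional effect, and type I error is kept.
- **The viral-load model already gives a load-adjusted antiviral test, and is a weak precedent.** This stands in part. It codes baseline as study day 0, so baseline load appears to be both response and covariate. It also answers a different question from time to clearance.
- **The simulations favour adjustment.** This stands in part. Load acts linearly and is measured without error, and nobody starts negative. In the trial, swab type may differ between patients, and SAP 7.4 tabulates negative baseline tests. Adjusted HRs below 1.5 do not undermine the mechanism: with daily testing in A, at prognostic HRs of 1.25 to 2.5, they are 1.501 to 1.515, so the remaining gap comes from the few visit days.
- **Adding the covariate could drop ITT patients with no quantitative Day 1 value.** This is a real cost, and the remedy must prevent it.

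What does not stand is that this is mere preference. The SAP already plans to use this baseline value, adding it costs essentially nothing if load is not prognostic, and a choice made after unblinding would not be credible.

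**Conclusion.** The omission is real and its consequence is limited. The planned Cox analysis of clearance is a valid test of one secondary endpoint. If baseline load is prognostic, the analysis is less efficient than it could be, and its HR is attenuated relative to the load-conditional HR.

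Under an assumed true HR of 1.5 and assumed prognostic HRs of about 1.25 to 2.7 per SD, the loss is roughly 3 to 18 points of power at one-sided 0.025 and 0 to 13 points at one-sided 0.2, with an HR shift of about 0.02 to 0.12. There is no loss if load is not prognostic, and no gain is available without quantitative results.

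A reader might go further and see a contradiction between the two models of SAP 7.6.2.3. There is none: Protocol 8.3 permits the smaller covariate set, and the viral-load model runs only when quantitative data exist.

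**What to change.** Add to SAP 7.6.2.3, before unblinding:

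*If quantitative results are available, natural-log baseline viral load (negatives at half the lower limit of detection) will be added to the Cox model for time to virological clearance. ITT patients with no quantitative Day 1 value will be retained by using the overall mean and a missing-value indicator. The model without viral load will be reported alongside, and will be the only analysis if quantitative results are not available.*

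The mean-plus-indicator method is one example; any simple prespecified method that keeps the ITT set whole will serve. Record the added covariate in SAP section 8, which now states that the methods do not differ from the protocol. Protocol 8.3 leaves room for it.

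The cost is a few sentences and a small amount of extra analysis, with no new sampling. The downside is that the analysis of one secondary endpoint then depends on assay availability. The half-limit value gives patients who are already negative on Day 1 a covariate, but does not settle whether they are at risk of clearance; that is a separate question.
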